3. STUDY DESIGN

This is a randomized, double-blind, placebo-controlled, parallel-group study which is 16 weeks in duration. The study is designed to evaluate the safety and efficacy of lebrikizumab when used in combination with TCS treatment compared with placebo in combination with TCS treatment for moderate-to-severe AD (Figure 1).

Eligible adult and adolescent patients (≥ 12 to < 18 years and weighing ≥ 40 kg) with moderate-to-severe AD for at least one year, defined according to the American Academy of Dermatology Consensus Criteria, an EASI of ≥ 16 , an IGA score of ≥ 3 and a BSA of $\geq 10\%$ will be enrolled.

During the 16-week treatment period, approximately 225 patients will be stratified and randomized 2:1 to treatment with either 250 mg lebrikizumab (loading dose of 500 mg given at Baseline and Week 2) or placebo by subcutaneous (SC) injection every 2 weeks (Q2W). All study drug injections will be administered in the clinic. TCS will be initiated at Baseline in all patients and may be tapered or stopped, as needed, based on treatment response.

Efficacy will be measured through IGA, EASI, SCORAD, BSA, Pruritus and Sleep-loss scores and, TCS/TCI use.

Safety will be assessed by monitoring adverse events, serum chemistry, hematology and urinalysis laboratory testing, physical examination, pulse and blood pressure. An independent Data Safety Monitoring Board will monitor patient safety by conducting formal reviews of accumulated safety data periodically throughout the trial.

Quality of life and impact of disease will be assessed using the POEM, DLQI/CDLQI, EQ-5D, and PROMIS[®] Anxiety and Depression measures. Patients reporting comorbid asthma at study entry will complete the ACQ-5.

Serum samples will be collected for pharmacokinetic analysis and immunogenicity.

After completion of the Week 16 visit, patients will be offered the option to continue treatment in a separate long-term extension study (DRM06-AD07).

Patients who early terminate or choose not to enter the long-term extension study will receive a safety follow-up approximately 12 weeks after the last study drug injection.

Completion of Patient Participation: A patient is considered to have completed the study if he/she has completed the last scheduled visit:

- For subjects continuing into LTE, upon completion of week 16 visit and rolling into LTE study
- For subjects not continuing into LTE, when subject had either week 16 or ET visit, and safety follow up visit (12 weeks after last IP administration)

The end of the study is defined as the date of the last visit of the last patient in the study shown in the Schedule of Visits and Procedures.

Figure 1: Study Schema

3.1. Duration of the Study

The total duration of a patient's participation in this study, if enrolling in the LTE, will be approximately 20 weeks (Screening: maximum duration of 30 days; Treatment Period: 16 weeks).

The total duration of a patient's participation in this study if not enrolling in the long-term extension will be approximately 30 weeks (Screening: maximum duration of 30 days; Treatment Period: 16 weeks; Post-Treatment Follow-up: 12 weeks from last dose).

3.2. Study Population and Number of Patients

Approximately 225 patients with moderate to severe atopic dermatitis, including approximately 50 adolescent patients (≥ 12 to < 18 years, weighing ≥ 40 kg).

4. SELECTION OF PATIENTS

Prospective approval of protocol deviations to recruitment and enrollment criteria, also known as protocol waivers or exemptions, is not permitted.

4.1. Inclusion Criteria

Patients must meet all the following criteria to be eligible for this study:

1. Adults and adolescents (≥ 12 to < 18 years of age and weighing ≥ 40 kg).
2. Chronic AD (according to American Academy of Dermatology Consensus Criteria) that has been present for ≥ 1 year before the screening visit (see [Appendix 2](#)).
3. Eczema Area and Severity Index (EASI) score ≥ 16 at the baseline visit
4. Investigator Global Assessment (IGA) score ≥ 3 (scale of 0 to 4) at the baseline visit (see Section [8.2.1](#)).
5. $\geq 10\%$ body surface area (BSA) of AD involvement at the baseline visit

6. History of inadequate response to treatment with topical medications.
7. Applied a stable dose of non-medicated topical moisturizer at least twice daily for ≥ 7 days prior to the baseline visit.
8. Completed electronic diary entries for pruritus and sleep-loss for a minimum of 4 of 7 days preceding randomization.
9. Willing and able to comply with all clinic visits and study-related procedures and questionnaires.
10. For women of childbearing potential: agree to remain abstinent (refrain from heterosexual intercourse) or use a highly effective contraceptive method during the treatment period and for at least 18 weeks after the last dose of lebrikizumab or placebo.

NOTE: A woman of childbearing potential (WOCBP) is defined as a postmenarcheal female, who has not reached a postmenopausal state (≥ 12 continuous months of amenorrhea with no identified cause other than menopause), and has not undergone surgical sterilization (removal of ovaries and/or uterus).

NOTE: The following are highly effective contraceptive methods: combined (estrogen and progestogen containing) hormonal contraception (oral, intravaginal, transdermal) associated with inhibition of ovulation, progestogen-only hormonal contraception (oral, injectable, implantable) associated with inhibition of ovulation, intrauterine device (IUD), intrauterine hormone-releasing system (IUS), bilateral tubal occlusion, vasectomized partner, or sexual abstinence. The reliability of sexual abstinence should be evaluated in relation to the duration of the clinical trial and the preferred and usual lifestyle of the patient. Periodic abstinence (e.g., calendar, ovulation, symptothermal, or postovulation methods) and withdrawal are not acceptable methods of contraception.

11. Male patients must agree to use an effective barrier method of contraception during the study and for a minimum of 18 weeks following the last dose of study drug if sexually active with a female of child bearing potential.
12. Provided signed informed consent/assent as described in Section 10.15.

4.2. Exclusion Criteria

Patients meeting any of the criteria below will be excluded from this study:

1. Participation in a prior lebrikizumab clinical study.
2. History of anaphylaxis as defined by the Sampson criteria ([Sampson 2006](#)).
3. Treatment with topical corticosteroids, calcineurin inhibitors or Phosphodiesterase-4 inhibitors such as crisaborole within 1 week prior to the baseline visit.
4. Treatment with any of the following agents within 4 weeks prior to the baseline visit:
 - a. Immunosuppressive/immunomodulating drugs (e.g., systemic corticosteroids, cyclosporine, mycophenolate-mofetil, IFN- γ , Janus kinase inhibitors, azathioprine, methotrexate, etc.)
 - b. Phototherapy and photochemotherapy (PUVA) for AD.

5. Treatment with the following prior to the baseline visit:
 - a. An investigational drug within 8 weeks or within 5 half-lives (if known), whichever is longer.
 - b. Dupilumab within 8 weeks.
 - c. B Cell-depleting biologics, including rituximab, within 6 months.
 - d. Other biologics within 5 half-lives (if known) or 16 weeks, whichever is longer.
6. Use of prescription moisturizers within 7 days of the baseline visit.
7. Regular use (more than 2 visits per week) of a tanning booth/parlor within 4 weeks of the screening visit.
8. Treatment with a live (attenuated) vaccine within 12 weeks of the baseline visit or planned during the study.
9. Uncontrolled chronic disease that might require bursts of oral corticosteroids, e.g., co-morbid severe uncontrolled asthma (defined by an ACQ-5 score ≥ 1.5 or a history of ≥ 2 asthma exacerbations within the last 12 months requiring systemic [oral and/or parenteral] corticosteroid treatment or hospitalization for > 24 hours).
10. Active chronic or acute infection requiring treatment with systemic antibiotics, antivirals, antiparasitics, antiprotozoals, or antifungals within 2 weeks before the baseline visit, or superficial skin infections within 1 week before the baseline visit.

NOTE: patients may be rescreened after infection resolves.
11. Evidence of active acute or chronic hepatitis (as defined by the Department of Health & Human Services Centers for Disease Control and Prevention) or known liver cirrhosis.
12. Diagnosed active endoparasitic infections or at high risk of these infections.
13. Known or suspected history of immunosuppression, including history of invasive opportunistic infections (e.g., tuberculosis [TB], histoplasmosis, listeriosis, coccidioidomycosis, pneumocystosis, and aspergillosis) despite infection resolution: or unusually frequent, recurrent, or prolonged infections, per the Investigator's judgment.
14. History of human immunodeficiency virus (HIV) infection or positive HIV serology at screening.
15. In the Investigator's opinion, any clinically significant laboratory results from the chemistry, hematology or urinalysis tests obtained at the screening visit.
16. Presence of skin comorbidities that may interfere with study assessments.
17. History of malignancy, including mycosis fungoides, within 5 years before the screening visit, except completely treated in situ carcinoma of the cervix, completely treated and resolved non-metastatic squamous or basal cell carcinoma of the skin.
18. Severe concomitant illness(es) that in the Investigator's judgment would adversely affect the patient's participation in the study. Any other medical or psychological condition that in the opinion of the Investigator may suggest a new and/or insufficiently understood disease, may present an unreasonable risk to the study patient because of his/her

participation in this clinical trial, may make patient's participation unreliable, or may interfere with study assessments.

19. Pregnant or breastfeeding women, or women planning to become pregnant or breastfeed during the study.
20. Have had an important side effect to TCS (e.g., intolerance to treatment, hypersensitivity reactions, significant skin atrophy, and systemic effects), as assessed by the investigator or treating physician that would prevent further use.

5. STUDY DRUG

5.1. Investigational Medicinal Product

Lebrikizumab is a sterile liquid solution containing 125 mg/mL lebrikizumab, histidine acetate, sucrose, polysorbate 20, and sterile water for injection, USP, pH 5.4–6.0. Placebo solution is identical in appearance and content to the active solution except for lebrikizumab. All study drug (lebrikizumab and placebo) will be supplied as a sterile pre-filled syringe with a pre-assembled needle safety device (PFS-NSD). Each pre-filled syringe is intended for a single 2 mL dose (250 mg) administered subcutaneously (SC).

5.2. Storage and Labeling

Study drug is to be stored under refrigerated conditions (2–8°C) and protected from excessive light and heat. Study drug should not be frozen, shaken or stored at room temperature. Temperature excursions outside of 2–8°C must be reported to the Sponsor or the designee.

Each PFS-NSD will be packaged in a carton. A medication numbering system will be used in labeling blinded study drug. Lists linking medication numbers with product lot numbers will be maintained by the group responsible for study drug packaging. In order to maintain the study blind, these lists will not be accessible to individuals involved in study conduct.

Medication numbers will be assigned to a patient in the electronic data capture system based on the study randomization schema.

5.3. Patient Randomization

Patients will be assigned a unique identifier by the sponsor. Any patient records, datasets or tissue samples that are transferred to the sponsor will contain the identifier only; patient names or any information which would make the patient identifiable will not be transferred. All patients will be randomly allocated to receive the study treatment using an electronic data capture system (an electronic randomization and trial supply management system) at the Baseline visit. The allocation to treatment will be prospectively stratified by geographic region (US versus EU versus rest of world), age (adolescent patients 12 to <18 years versus adults ≥18 years) and disease severity (IGA 3 versus 4). At the Baseline visit (Day 1), once a patient is considered eligible to participate in the study, demographic and stratification information will be entered into the EDC to receive a medication number assigning the appropriate treatment to a patient. Patients will be randomized 2:1 to one of the following treatment groups:

- Lebrikizumab 250mg Q2W: 500mg lebrikizumab administered at Baseline and Week 2 (loading dose) and 250mg given every two weeks (Q2W) through Week 14. TCS treatment initiated at Baseline and applied PRN.
- Placebo 4mLs (two PFS-NSD) administered at Baseline and Week 2 and 2mLs given Q2W through Week 14. TCS treatment initiated at Baseline and applied PRN.

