9.12. Sample-Size Determination

For FDA

Approximately 225 patients will be randomized at a 2:1 ratio to lebrikizumab or placebo (150 patients:75 patients). The assumed IGA score of 0 or 1 at Week 16 response rates are 38% for lebrikizumab 250 mg Q2W and 13% for placebo. The assumption for lebrikizumab is based on the DRM06-AD01 Phase 2b study, the proportion of patients who achieved an IGA score of 0 or 1 at Week 16 using the rescue medication non-response sensitivity analysis, adjusting for the allowed use of TCS/TCI. The placebo response rates are based on the review of historical TCS clinical studies in atopic dermatitis (Simpson et al. 2016). This study has power >95% for testing superiority of lebrikizumab to placebo based on a two-sided Fisher's exact test with alpha of 0.05.

For EMA:

Approximately 225 patients will be randomized at a 2:1 ratio to lebrikizumab or placebo (150 patients:75 patients). The assumed IGA score of 0 or 1 at Week 16 response rates are 38% for lebrikizumab 250 mg Q2W and 13% for placebo. The assumed EASI75 response rate at Week 16 response rates are 58% for lebrikizumab 250 mg Q2W and 20% for placebo. The assumptions for lebrikizumab are based on the DRM06-AD01 Phase 2b study, the proportion of patients who achieved an IGA score of 0 or 1 and proportion of patients who achieved EASI75 response at Week 16 using the rescue medication non-response sensitivity analysis, adjusting for the allowed use of TCS/TCI. The placebo response rates are based on the review of historical TCS clinical studies in atopic dermatitis (Simpson et al. 2016). This study has power >95% for testing superiority of lebrikizumab to placebo based on a two-sided Fisher's exact test with alpha of 0.05.

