### 6.3. Adjustments for Covariates

Unless otherwise specified, the statistical analysis models for the Treatment Period efficacy and health outcome analysis will include the following stratification factors for Baseline randomization: geographic region (US versus EU versus rest of world), age group (adolescent patients 12 to <18 versus adults  $\geq 18$  years) and baseline disease severity (IGA 3 versus 4).

Below are the country allocations within each geographic region.

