#### **6.4.1. Primary Analysis - Markov Chain Monte Carlo Multiple Imputation (MCMC-MI)**

The primary method of handling missing efficacy data relative to the primary estimand will be as follows for both binary and continuous endpoints:

For patients who receive rescue medication (high-potency TCS or systemic AD treatment, defined in [Appendix 2](#)) or discontinue treatment due to lack of efficacy, set to the patient's baseline value subsequent to this time through Week 16. The MCMC-MI will be used to handle the remaining missing data. Imputation will be conducted within each treatment group independently so the pattern of missing observations in one treatment group cannot influence missing value estimations in another. The SAS PROC MI with the MCMC option will be used to conduct the MCMC-MI. The imputation model will include the relevant baseline and postbaseline.

For each imputation process, 25 datasets with imputations will be calculated. The initial seed values are given in [Table KGAD.6.6](#). Each complete data set will be analyzed with the specified analysis. The results from these analyses will be combined into a single inference using SAS PROC MIANALYZE.

Cochran-Mantel-Haenszel (CMH) test statistic will be transformed using the Wilson-Hilferty transformation and then standardized (Ratitch 2013) prior to combining them using SAS PROC MIANALYZE. Details of combining estimates and test statistics for categorical endpoints with multiple imputation can be found in [Appendix 3](#).

For binary responses related to EASI and IGA, the binary response variables will be calculated based on the multiply imputed datasets that have been created. Because the MCMC algorithm is based on the multivariate normal model, imputed values for IGA will not generally be one of the discrete values used in IGA scoring (0, 1, 2, 3, or 4). Therefore, to derive the binary IGA response variable, standard rounding rules will be applied to the imputed values. For example, if a patient has an IGA score imputed as 1.4 (and assuming a Baseline IGA score of 3), the imputed value would be rounded down to 1, and the minimum change from Baseline of 2 would have been met. This patient would be considered a responder.

For derivation of an EASI-75 and EASI-90 response, no rounding will be performed. The imputed Week 16 EASI value will be compared directly to the observed Baseline EASI value to determine whether a reduction of at least 75% or 90% was achieved.

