## 6.15. Subgroup Analyses

### 6.15.1. Efficacy Subgroup Analyses

Subgroup analyses will be conducted for the primary endpoints IGA 0,1 and EASI-75 at Week 16 in the mITT Population using MCMC-MI approach as in primary analysis (Section 6.4.1). A logistic regression analysis with treatment, subgroup, and treatment-by-subgroup interaction as factors will be used. The treatment-by-subgroup interaction will be tested using the Firth correction (Firth 1993) at the 10% significance level. Treatment group differences will be evaluated within each subgroup using the chi-square test, regardless of whether the interaction is statistically significant. If any group within the subgroup (for example, yes, no) is <10% of the total population, only descriptive statistics will be provided for that subgroup (that is, no inferential testing).

Forest plots may be created to illustrate the treatment differences with 95% CIs between each of the lebrikizumab treatment groups and placebo group, by each subgroup category.

The following subgroups will be analyzed:

- Age group (12<18, ≥18)
- Age group (Adolescents (12<18), Adults ≥18 to < 65, ≥65 to < 75, ≥75)
- Sex (male, female)
- Race (American Indian or Alaska Native, Asian, Black or African American, Native Hawaiian or Other Pacific Islander, White, Multiple, Other, Not Reported)
- Ethnicity (Hispanic or Latino, Not Hispanic or Latino, Not reported, Unknown) for US patients
- Region (as defined in Section 6.5)
- Weight category (<60 kg, ≥60 to <100 kg, ≥100 kg)

- BMI category Underweight ( $<18.5$  kg/m^2), Normal ( $\geq 18.5$  and  $<25$  kg/m^2), Overweight ( $\geq 25$  and  $<30$  kg/m^2), Obese ( $\geq 30$  and  $<40$  kg/m^2), Extreme obese ( $\geq 40$  kg/m^2)
- Duration since AD onset category (0 to  $<2$  years, 2 to  $<5$  years, 5 to  $<10$  years, 10 to  $<20$  years,  $\geq 20$  years)
- Baseline IGA 3 versus 4
- Baseline pruritus  $<4$  versus  $\geq 4$
- Prior use of systemic treatment (yes, no)

Some additional subgroup analyses may be added to meet regulatory requirement. The analysis of additional subgroups will not require an amendment to the SAP.

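### The imputation model in SAP 6.4.1 names neither age group nor region, yet the subgroup and region-interaction analyses reuse its imputations; adding the randomisation factors is a cheap improvement.

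*Protocol*

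**What the plan says.** **Randomisation.** Protocol 5.3: "The allocation to treatment will be prospectively stratified by geographic region (US versus EU versus rest of world), age" group and baseline IGA (3 versus 4).

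**Analysis.** SAP 6.3 makes adjustment the default: "the statistical analysis models for the Treatment Period efficacy and health outcome analysis will include the following stratification factors", followed by the same three factors. SAP Appendix 3 stratifies the Cochran-Mantel-Haenszel (CMH) test, common risk difference and odds ratio by all three.

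**Imputation.** SAP 6.4.1 sets rescue use and discontinuation for lack of efficacy to baseline. The remaining missing values are imputed by MCMC, separately by arm. Its whole description of the model is "The imputation model will include the relevant baseline and postbaseline". Protocol 9.3 names no covariates either. In Table KGAD.6.6 the two endpoints that combine pruritus with IGA or EASI use a separate joint imputation of five measures; the table lists no stratification factor.

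**Reuse.** SAP 6.15.1 analyses IGA 0/1 and EASI-75 by age, region, baseline IGA and other subgroups at "Week 16 in the mITT Population using MCMC-MI approach as in primary analysis". SAP 6.5 sets aside a treatment-by-site model and relies on region, with an interaction test at the 10% level. Protocol 3.2 plans for about 225 patients, "including approximately 50 adolescent patients".

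**The concern.** Imputing within arm protects the overall treatment difference. It does not protect differences between subgroups inside an arm. Without an age term, a missing adolescent value is drawn from a relationship fitted mostly to adults (about 225 − 50 = 175 of 225). Any part of the adolescent response not already visible in earlier scores is replaced by the arm's average pattern. The same mechanism applies to region.

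At stake are the adolescent and regional estimates and their interaction tests. Region also stands in for site when consistency is judged. The planned subgroup analyses use only this imputation: the nonresponder analysis is specified for the overall comparison, and the tipping-point analysis varies response probabilities by arm, not by subgroup.

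There is a pre-specification gap as well. The seeds are fixed to the digit but the variable list is not, so two programmers could build different models for the primary analysis.

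**Working it through.** **Step 1. The plan's own figure.** Protocol 9.12 gives: "Approximately 225 patients will be randomized at a 2:1 ratio to lebrikizumab or placebo (150 patients:75 patients"), with IGA 0/1 "response rates are 38% for lebrikizumab 250 mg Q2W and 13% for placebo" and EASI-75 "58% for lebrikizumab 250 mg Q2W and 20% for placebo". Exact enumeration of the two-sided Fisher test at 0.05 gives power of 98.4% for IGA 0/1 and 99.99% for EASI-75, so the stated >95% reproduces. The plan gives no figure for subgroup attenuation.

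**Step 2. Simulation inputs.** From the documents: adolescent share 50/225 = 22%; overall effect 38% − 13% = 25 points; imputation within arm; imputed IGA rounded, so a value below 1.5 counts as a response. Assumed, because the documents are silent: the share of outcomes left to imputation (5–30%), the timing of dropout, the within-patient correlation (two structures), and a true adult-minus-adolescent gap in treatment effect of about 17 or 32 points. The run used 400,000 patients per arm with a baseline and eight visits. Imputation was by regression on the measure's own scores, without and then with age group.

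**Step 3. Gap without age in the model.** Loss = (full-data gap − imputed gap) / full-data gap. Gaps are in percentage points, and losses are computed from the rounded gaps.

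| Assumed gap | Missing | Mildest setting (dropout spread to Week 14) | Harshest setting (dropout by Week 2) |
|---|---|---|---|
| 17 | 10% | 16.7 → 16.0: 0.7/16.7 = 4% | 16.8 → 15.2: 1.6/16.8 = 10% |
| 17 | 20% | 16.2 → 14.9: 1.3/16.2 = 8% | 17.0 → 13.8: 3.2/17.0 = 19% |
| 32 | 10% | 31.8 → 30.6: 1.2/31.8 = 4% | 32.2 → 29.4: 2.8/32.2 = 9% |
| 32 | 20% | 32.4 → 30.1: 2.3/32.4 = 7% | 32.5 → 26.8: 5.7/32.5 = 18% |

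Across both gaps the loss is 4–10% at 10% missing and 7–19% at 20%. At 5% missing it is 2–5%, and at 30% it is 11–28%.

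**Step 4. With age in the model.** The gap returns to within about 0.2 points of its full-data value in every setting. The overall effect stays at about 25 points with or without age.

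**Step 5. Trial-size check.** A separate simulation of 400 trials at N = 225 with 15% missing gave a mean gap of 20.8 points on full data, 18.6 without the strata and 20.4 with them. The loss without strata is 2.2/20.8 = 11%. The SD of the overall risk difference was 5.7 points either way.

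**Step 6. Against sampling error.** At 2:1, 175 adults split about 117:58 and 50 adolescents about 33:17. Take placebo response 13% in both, an adult effect of 28.7 points and an adolescent effect of 12.0 points:

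SE² = 0.417×0.583/117 + 0.13×0.87/58 + 0.25×0.75/33 + 0.13×0.87/17 = 0.00208 + 0.00195 + 0.00568 + 0.00665 = 0.01636

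SE = 12.8 points, about 13. For the 17-point gap, the shift of 0.7 to 3.2 points is 0.7/12.8 = 0.05 to 3.2/12.8 = 0.25 of a standard error.

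**The case against.** The strongest reply is that the plan is incomplete rather than restrictive. The sentence in SAP 6.4.1 breaks off, says the model will include certain terms rather than be limited to them, and could be read to cover baseline factors. That stands: a reader might infer a deliberate choice of the measure's own scores alone, and the text does not establish one. For the two composite endpoints that inference is wrong, since they are imputed jointly with other measures.

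Other tempting readings also go too far:

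- *All efficacy models use the strata.* SAP 6.3 states a default. The subgroup logistic model and within-subgroup chi-square tests in SAP 6.15.1 do not list the strata.
- *Subgroup results are biased toward no difference.* This holds only if a true difference exists beyond what earlier scores carry. Protocol 1.4 expects adults and adolescents to respond similarly; with no gap, nothing is attenuated.
- *The IGA-severity interaction is erased.* For the IGA endpoint, baseline IGA is the measure's own baseline and each arm has its own slope, so that interaction is largely carried.
- *European outcomes are drawn from other regions' patients.* The documents give no regional sample sizes.
- *The primary result is exposed.* It hardly moves, and the subgroup analyses lie outside the multiplicity-controlled family. If any category holds under 10% of patients, that subgroup is descriptive only.

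The size is also bounded, because only discontinuation for other reasons and intermittent gaps reach the imputation. None of this removes the remaining point: the factors are fully observed, they define the subgroups being tested, and they are not named in the model.

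**Conclusion.** The concern holds as a low-severity, cheap improvement. SAP 6.4.1 should name age group and region in the imputation model, because the age and region analyses are run on its output. Given a true age difference, the loss is about 4–10% of the gap at 10% missing and 7–19% at 20%, and adding the factor recovers almost all of it. In points this is roughly 1 to 3 for a 17-point gap and up to 5.7 for a 32-point gap in the harshest 20% setting, against a sampling standard error of about 13. The overall comparison is essentially unchanged.

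The figures rest on an assumed missing share, dropout timing, correlation and gap. Only age was quantified; the argument for region is by the same mechanism.

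**What to change.** **Change to SAP 6.4.1.** Complete the sentence along these lines: the imputation model, run within each treatment group, will include geographic region, age group and baseline IGA stratum (the last where IGA is not itself the measure), together with the baseline and post-baseline values of the measure. Enter the factors as fully observed 0/1 indicators in PROC MI.

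**Joint imputation.** Add the same factors to the joint model in Table KGAD.6.6. Keep it separate, as planned; one imputed dataset for everything would contradict that table.

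**Sparse-cell rule.** Drop or collapse an indicator that is constant or too sparse within an arm, and report where this was done. DLQI is the clearest case: patients aged 16 or under complete CDLQI, so only 17-year-olds would carry the adolescent indicator. A small region is another.

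**Cost.** A sentence or two of text, and a few extra parameters in a placebo arm of about 75. Feasibility was not tested for DLQI or the joint model, which is why the rule is needed. If a factor is left out on purpose, state the reason.
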